3.9 Definition of an intercurrent event

Handling of intercurrent events is one of the key elements for the analysis of efficacy endpoints.

An intercurrent event is defined as receipt of systemic antibiotic rescue medication or discontinuation of study treatment due to an AE or lack of efficacy (See Section 8.2.2).

Receipt of systemic antibiotic rescue medication is defined as initiating any systemic antibiotic on or after Baseline for any reason (including in response to an AE). The only exception to this rule is if a participant randomized to the antibiotic stratum on a tetracycline antibiotic interrupts their stable dose of tetracycline antibiotic during the study and subsequently restarts the same tetracycline antibiotic as confirmed using the coded preferred term. The restarted dose and frequency of the antibiotic must be the same or lower than the regimen prior to the interruption.

The dates of an intercurrent event are as follows:

- For receipt of systemic antibiotic rescue medication: start date of the antibiotic
- For discontinuation of study treatment due to an AE or lack of efficacy: Last study treatment date + 17 days. Note: study treatment discontinuation includes study discontinuation.

The choice of 17 days is intended to capture the interval between dosing and lesion assessments (14 days), as well as the visit window (3 days).

An additional sensitivity analysis will be conducted where missing data due to COVID-19 will be considered an intercurrent event and will be imputed as a nonresponse at that particular visit. This will be identified when there are missing data at a visit that has been impacted by COVID-19 according the COVID-19 impact CRF page. The date of this intercurrent event will be the date of the impacted visit.

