4.2.1.1 Handling missing data for the primary efficacy endpoint

If study participants have an intercurrent event as defined in Section 3.9, then the primary efficacy variable at that timepoint and all subsequent timepoints (whether the data were observed or not) will be set to “nonresponse” as the study participant has not met the criteria for response based on the composite estimand defined in Section 8.2. All remaining missing data for the endpoint will be imputed using multiple imputation Markov-Chain Monte Carlo method (MI-MCMC)/monotone regression for the primary analysis.

In addition, sensitivity analyses using NRI, MI-MCMC/reference-based methods, tipping point analysis, and observed case (OC) methods will be performed, which will assess the impact of different methods of handling missing data.

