4.2.1.3 Handling missing data for the other efficacy endpoints

For other binary efficacy endpoints, missing data will be imputed using the same method as the primary efficacy endpoint. NRI and OC methods will be performed as sensitivity analyses of HiSCR₅₀, HiSCR₇₅, HiSCR₉₀, and HiSCR₁₀₀.

For other continuous efficacy endpoints, the MI-MCMC/monotone regression method will be used to impute missing data as the primary method, regardless of whether the missing data are preceded by an intercurrent event. That is, if an intercurrent event occurs on or before a visit, the result for that visit will be treated as missing and imputed with the missing data. If the imputation model cannot converge, LOCF will be used.

For other ordinal endpoints (EQ-5D-3L, PGI-S-HS, PGI-C-HS, PGI-S-SP, PGI-C-SP), the OC method will be applied as the primary analysis method. No imputation is applied.

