4.2.3.1 Composite estimand

A composite estimand strategy as defined in Section 8.2.2 allows incorporation of the two intercurrent events (eg, receipt of systemic antibiotic rescue medication or discontinuation of study treatment due to an AE or lack of efficacy) within the definition of the endpoint. These intercurrent events are considered meaningful to the efficacy outcome following receipt of study medication. For example, within the proposed composite estimand framework, a randomized study participant who discontinues from study treatment due to lack of efficacy prior to Week 16 will be considered a treatment failure at Week 16 regardless of the lesion count assessment performed at that visit.

The assumptions and robustness of the primary analysis (modified composite estimand as defined in Section 8.2.2) will be assessed through the sensitivity analyses defined in Section 8.2.3. The impact of intercurrent event handling and data imputation methods on endpoint derivation will also be assessed via the analyses of lesion counts and derived HiSCR variables as specified in Section 8.4.2.1 and Section 8.4.1.1, respectively.

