8.4.1.2 Time to response of HiSCR₂₅, HiSCR₅₀, HiSCR₇₅, HiSCR₉₀, and HiSCR₁₀₀

See Section 8.4.1.1 for the derivation of HiSCR.

Initial Treatment Period

Time to HiSCR₂₅, HiSCR₅₀, HiSCR₇₅, HiSCR₉₀, and HiSCR₁₀₀ (in days) during the Initial Treatment Period will each be calculated as:

Min (Date of first HiSCR_{xx} response, Date of Week 16 visit) – Date of first dose of study medication + 1, here xx represents 25, 50, 75, 90, 100 respectively. All visits including unscheduled visits are considered.

Participants who discontinue study treatment without achieving a given HiSCR response prior to Week 16 visit will be censored at the date of last lesion count assessment. Participants who reach the Week 16 Visit without achieving the given response will be censored at the date of the Week 16 Visit. Participants who experience an intercurrent event prior to achieving a HiSCR response will be censored at the date of the intercurrent event. Participants will be censored at Baseline if there is no Baseline lesion count assessment or no Post-Baseline lesion count assessment.

Time to HiSCR₂₅, HiSCR₅₀, HiSCR₇₅, HiSCR₉₀, and HiSCR₁₀₀ response during Initial Treatment Period will each be estimated and presented using the Kaplan-Meier product-limit method for each treatment group.

Kaplan-Meier plots of time to HiSCR responses will be presented by treatment group. In these Kaplan-Meier plots, the line will start at 0 (since there are no responders at Week 0) and will increase over time, representing time to achieving the response.

The median time to response, including the 2-sided 95% confidence interval, will be calculated for each treatment. Comparisons of bimekizumab vs placebo will be analyzed using a log-rank test stratified by Hurley Stage at Baseline and Baseline antibiotic use.

Combined Initial and Maintenance Treatment Period

An additional time to HiSCR_{25} , HiSCR_{50} , HiSCR_{75} , HiSCR_{90} , and HiSCR_{100} (in days) during the combined Initial and Maintenance Treatment Period will be calculated as above, where the Week 48 visit is considered instead of Week 16.

Time to HiSCR_{25} , HiSCR_{50} , HiSCR_{75} , HiSCR_{90} , and HiSCR_{100} response during the combined Initial and Maintenance Treatment Period will each be estimated and presented using the Kaplan-Meier product-limit method for each treatment group.

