8.4.1.4 HiSCR_{50} , HiSCR_{75} , HiSCR_{90} , and HiSCR_{100} among Week 16 Responders

See Section 8.4.1.1 for the derivation of HiSCR response.

Summaries of HiSCR_{50} , HiSCR_{75} , HiSCR_{90} , and HiSCR_{100} responders at each visit from Week 16 through Week 48 will be summarized based on a subset of participants in the MS who achieve response at Week 16. The summaries will be as follows:

- HiSCR_{50} responder rate based on participants who achieved HiSCR_{50} response at Week 16
- HiSCR_{75} responder rate based on participants who achieved HiSCR_{75} response at Week 16
- HiSCR_{90} responder rate based on participants who achieved HiSCR_{90} response at Week 16
- HiSCR_{100} responder rate based on participants who achieved HiSCR_{100} response at Week 16

Line plots of the above HiSCR responder rate categories over time (from Week 16 to Week 48), by treatment group, will be produced.

8.4.1.5 Time to loss of response of HiSCR_{50} , HiSCR_{75} , HiSCR_{90} , and HiSCR_{100} in Week 16 responders

See Section 8.4.1.1 for the derivation of HiSCR response.

Time to loss of response will be based on the MS and include only participants who had the corresponding HiSCR response at Week 16 (considering intercurrent event handling from the composite estimand described in Section 8.2.2).

Time to loss of response of HiSCR₅₀, HiSCR₇₅, HiSCR₉₀, and HiSCR₁₀₀ (in days) is defined as:
Date of loss of response of HiSCR₅₀, HiSCR₇₅, HiSCR₉₀, and HiSCR₁₀₀ - Date of Week 16 treatment administration + 1.

Time to loss of response will be estimated and presented using the Kaplan-Meier product-limit method for each treatment. Participants who experience an intercurrent event prior to loss of response will be considered as having lost response on the date of intercurrent event. Participants who reach the Week 48 Visit without loss of response will be censored at the date of the Week 48 Visit. Participants who discontinue treatment or study, for reasons other than those already defined for an intercurrent event, and who have not yet displayed loss of response by the time of withdrawal, will be censored at the date of the last lesion count assessment.

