8.4.4 Flare relative to Baseline

See Section 8.4.3 for the derivation of flare.

Disease flare status will be summarized by treatment group and visit using frequencies and percentages. The denominator for the percentage calculations will be the number of participants with non-missing data in each treatment group. This summary will also include the number of participants with any flare in the Initial Period, Maintenance Period, and the combined Initial and Maintenance Period. A bar chart of percentage of participants with flare, by visit and treatment, will be presented.

In addition, for each participant, the number of flares during the Initial Treatment Period will be calculated and summarized by treatment group. A corresponding histogram summarizing the number of flares during the Initial Treatment Period will be presented.

8.4.5 Time to flare by Week 16

See Section 8.4.3 for the derivation of flare.

Time to flare (in days) during the Initial Treatment Period will each be calculated as:

Min (Date of first flare, Date of Week 16 visit) – Date of first dose of study medication + 1.
All visits in the Initial Treatment Period including unscheduled visits are considered.

Participants who discontinue study treatment without experiencing a flare prior to Week 16 Visit will be censored at the date of last lesion count assessment. Participants who reach the Week 16 Visit without experiencing a flare will be censored at the date of the Week 16 Visit. Participants who experience an intercurrent event prior to experiencing a flare will be treated as experiencing a flare at the date of the intercurrent event. Participants will be censored at Baseline if there is no Baseline lesion count assessment or no Post-Baseline lesion count assessment.

Time to flare will be estimated and presented using the Kaplan-Meier product-limit method for each treatment group.

Kaplan-Meier plots of time to flare will be presented by treatment group. In these Kaplan-Meier plots, the line will start at 0 and will increase over time, representing time to achieving the response.

The median time to flare, including the 2-sided 95% confidence interval, will be calculated for each treatment. Comparisons of bimekizumab vs placebo will be analyzed using a log-rank test stratified by Hurley Stage at Baseline and Baseline antibiotic use.

8.4.6 Time to flare by Week 48

See Section 8.4.3 for the derivation of flare relative to Baseline.

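### Time to HiSCR response censors participants at rescue or at discontinuation for AE or lack of efficacy, so the curves run above the SAP's own definition of response

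*SAP*

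**What the plan says.** Section 8.4.1.2 defines time to HiSCR25, 50, 75, 90 and 100, first to Week 16 and then to Week 48. It uses Kaplan-Meier curves, a median with a 95% confidence interval and, to Week 16, a log-rank test stratified by Hurley Stage and antibiotic use. Its rule for the intercurrent event is: "Participants who experience an intercurrent event prior to achieving a HiSCR response will be censored at the date of the intercurrent event".

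Section 3.9 says what that event is: "An intercurrent event is defined as receipt of systemic antibiotic rescue medication or discontinuation of study treatment due to an AE or lack of efficacy".

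Other parts of the SAP handle the same event as follows:

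- Section 4.2.1.1, primary endpoint: "the primary efficacy variable at that timepoint and all subsequent timepoints (whether the data were observed or not) will be set to" nonresponse.
- Section 4.2.1.3: "For other binary efficacy endpoints, missing data will be imputed using the same method as the primary efficacy endpoint". Table 4-1 lists the other responder endpoints under the composite and observed-case columns, not under the hypothetical one.
- Section 4.2.3.1, rationale: "These intercurrent events are considered meaningful to the efficacy outcome following receipt of study medication".
- Section 8.4.1.3, response at both Weeks 16 and 48: a participant with any intercurrent event through Week 48 does not count as a responder.
- Section 8.4.1.5, time to loss of response: "Participants who experience an intercurrent event prior to loss of response will be considered as having lost response on the date of intercurrent event".
- Sections 8.4.5 and 8.4.6, time to flare: a participant with the event first "will be treated as experiencing a flare at the date of the intercurrent event".

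**The concern.** Kaplan-Meier is valid for the response curve only if participants censored at a given time have the same future chance of response as those who remain. A participant who stops for lack of efficacy, or needs antibiotic rescue, is not a neutral loss to follow-up. The SAP's own rationale says so. Under its handling of HiSCR, that participant cannot be a responder later. Censoring removes the participant from the denominator and shares the remaining probability among those still at risk, as though the participant might yet respond.

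At stake are ten Kaplan-Meier analyses (five thresholds, two periods), their medians, and the five stratified log-rank tests to Week 16. As written, they describe response in a setting without rescue or these discontinuations, and nothing in Section 8.4.1.2 tells the reader so.

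There is also an overlap within Section 8.4.1.2. A participant who discontinues treatment for an AE or lack of efficacy before responding meets two rules: censoring at the last lesion count, and censoring at the intercurrent event date, which Section 3.9 sets at the last treatment date plus 17 days. No order of precedence is given. Section 8.4.1.5 avoids this by limiting censoring to discontinuation for other reasons.

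**Working it through.** **Inputs.** Section 8.4.1.2 states no response rate and the SAP states no intercurrent event rate. For illustration I take the HiSCR50 rates of Table 2-1: 0.25 on placebo (N=70), 0.50 on Q4W (N=140) and 0.60 on pooled Q2W (N=280).

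**Check on those rates.** Two-proportion power, pooled variance under the null, two-sided alpha 0.025 (z = 2.241). For Q4W against placebo:

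- pooled proportion = (70×0.25 + 140×0.50)/210 = 0.4167
- null SE = √(0.4167×0.5833×(1/70 + 1/140)) = 0.0722
- alternative SE = √(0.25×0.75/70 + 0.50×0.50/140) = 0.0668
- power = Φ((0.25 − 2.241×0.0722)/0.0668) = 0.907; the plan states 0.90

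The same formula for Q2W gives 0.9996; the plan states 0.99. The rates are read correctly.

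**Size of the excess.** Let F be the share who respond before any intercurrent event by Week 16, and G the share who have the event before responding. F is the target under the SAP's handling of HiSCR. G is assumed, 5% to 30%. With constant hazards for both, Kaplan-Meier censoring at the event estimates

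1 − (1 − F − G)^(F/(F+G)).

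Example, F = 0.60 and G = 0.10: 1 − 0.30^(0.60/0.70) = 0.644, an excess of 4.4 points.

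| F | G=5% | G=10% | G=20% | G=30% | Excess, points |
|---|---|---|---|---|---|
| 0.25 | 0.257 | 0.265 | 0.283 | 0.304 | 0.7 to 5.4 |
| 0.50 | 0.516 | 0.534 | 0.577 | 0.634 | 1.6 to 13.4 |
| 0.60 | 0.621 | 0.644 | 0.701 | 0.785 | 2.1 to 18.5 |

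A simulation with eight two-weekly visits (assumed) and 400,000 participants agrees: at F = 0.60 and G = 0.10 it gives Kaplan-Meier 0.642 against an actual response share of 0.592.

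**Direction.** The Kaplan-Meier value is never below F, and is above it whenever a response follows an earlier censoring at the event. A higher curve crosses 50% sooner, so the median is too short. With F = 0.48 and G = 0.10 (assumed), Kaplan-Meier gives 1 − 0.42^(0.48/0.58), about 0.51. A median would then be reported although fewer than half responded.

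**Between-arm difference.** Q2W against placebo, true difference in F 0.60 − 0.25 = 0.35:

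| G placebo | G Q2W | Kaplan-Meier difference |
|---|---|---|
| 20% | 8% | 0.351 |
| 10% | 10% | 0.379 |
| 8% | 20% | 0.439 |

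The result turns on event rates by arm, which are unknown.

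**The case against.** The strongest reply is that no estimand is declared for time to response. Section 4.2.3 assigns the composite strategy to the primary and binary secondary endpoints, Section 4.2.1.3 carries the primary method to other binary endpoints, and Table 4-1 has no time-to-event row. Censoring at the event fits a hypothetical or while-on-treatment reading, and a log-rank test that censors a competing event is a recognised comparison of cause-specific hazards. This stands in part: the conflict is with how the SAP handles HiSCR elsewhere, not with a stated estimand for this endpoint. It does not remove the point, because Section 8.4.1.2 neither names such a strategy nor justifies independent censoring, and no responder endpoint is given a hypothetical strategy.

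Second, loss of response and flare are unfavourable, so the intercurrent event can itself count as the event. Response is favourable, so it cannot. A different mechanical rule is therefore needed, but censoring is not the only one available.

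Third, the composite time course is partly reported elsewhere. Section 8.4.1.1 plots HiSCR50 to HiSCR100 by visit with intercurrent events as nonresponse, and Section 8.4.12 gives time to intercurrent event by arm. That helps an alert reader but does not correct the response curves or their medians.

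Two stronger readings are tempting and are not supported. A reader might infer that the rule favours bimekizumab in the log-rank test. The SAP gives no event rates by arm, and the examples above range from almost no change to a clear one. A reader might also expect the corrected curve to match the by-visit responder rates. It would not, because Section 8.4.1.2 counts first response at any visit, including unscheduled ones.

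**Conclusion.** The point holds. Relative to the SAP's own definition of HiSCR response, censoring at the intercurrent event makes the Kaplan-Meier response curves too high and the median times to response too short in each arm. The direction does not depend on the assumed values. The size does: about 1 to 5 points at F = 0.25 and 2 to 18 points at F = 0.60 for G of 5% to 30%. The top of that range is extreme, since F = 0.60 with G = 0.30 leaves only 10% with neither event. F is borrowed from Week 16 rates, although time to first response is an ever-response measure. No direction can be given for the treatment comparison.

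The impact is limited. Time to response is an "other" efficacy endpoint, outside the testing procedure of Section 4.5 and absent from the nominal tests of Section 8.5. Primary and secondary conclusions do not change.

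**What to change.** In Section 8.4.1.2, treat an intercurrent event before response as nonresponse to the end of the period. Choose one of two implementations in advance:

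1. Report the cumulative incidence of response with the intercurrent event as a competing event.
2. Keep these participants in the risk set and censor them at the Week 16 or Week 48 visit date, or at the scheduled day if there is no visit.

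The two are close but not identical when other dropouts are censored early, so the SAP should name the one used. Derive the median and the stratified between-arm comparison from the same rule, and report the median as not reached where the curve stays below 50%.

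Limit censoring at the last lesion count to discontinuation for reasons other than an intercurrent event, as Section 8.4.1.5 does. This also removes the overlap between the two censoring dates. If a censor-at-event version is wanted, label it as a supplementary analysis under a hypothetical strategy.

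The cost is one censoring rule and its programming for ten analyses. No new data are needed. The reported response curves will be somewhat lower.

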8.4.1.4 HiSCR_{50} , HiSCR_{75} , HiSCR_{90} , and HiSCR_{100} among Week 16 Responders

See Section 8.4.1.1 for the derivation of HiSCR response.

Summaries of HiSCR_{50} , HiSCR_{75} , HiSCR_{90} , and HiSCR_{100} responders at each visit from Week 16 through Week 48 will be summarized based on a subset of participants in the MS who achieve response at Week 16. The summaries will be as follows:

- HiSCR_{50} responder rate based on participants who achieved HiSCR_{50} response at Week 16
- HiSCR_{75} responder rate based on participants who achieved HiSCR_{75} response at Week 16
- HiSCR_{90} responder rate based on participants who achieved HiSCR_{90} response at Week 16
- HiSCR_{100} responder rate based on participants who achieved HiSCR_{100} response at Week 16

Line plots of the above HiSCR responder rate categories over time (from Week 16 to Week 48), by treatment group, will be produced.

8.4.1.5 Time to loss of response of HiSCR_{50} , HiSCR_{75} , HiSCR_{90} , and HiSCR_{100} in Week 16 responders

See Section 8.4.1.1 for the derivation of HiSCR response.

Time to loss of response will be based on the MS and include only participants who had the corresponding HiSCR response at Week 16 (considering intercurrent event handling from the composite estimand described in Section 8.2.2).

Time to loss of response of HiSCR₅₀, HiSCR₇₅, HiSCR₉₀, and HiSCR₁₀₀ (in days) is defined as:
Date of loss of response of HiSCR₅₀, HiSCR₇₅, HiSCR₉₀, and HiSCR₁₀₀ - Date of Week 16 treatment administration + 1.

Time to loss of response will be estimated and presented using the Kaplan-Meier product-limit method for each treatment. Participants who experience an intercurrent event prior to loss of response will be considered as having lost response on the date of intercurrent event. Participants who reach the Week 48 Visit without loss of response will be censored at the date of the Week 48 Visit. Participants who discontinue treatment or study, for reasons other than those already defined for an intercurrent event, and who have not yet displayed loss of response by the time of withdrawal, will be censored at the date of the last lesion count assessment.

8.4.1.6 Partial response

See Section 8.2.1 for the derivation of AN count.

A partial response is defined as a $\geq 25\%$ reduction in AN count from Baseline (Week 0) at a particular timepoint.

The number and percentage of participants who are partial responders at Week 16 and become HiSCR₅₀, HiSCR₇₅, HiSCR₉₀, and HiSCR₁₀₀ responders in the Maintenance Treatment Period will be summarized by treatment group and visit. These analyses will be based on the subset of participants in the MS that are partial responders but not HiSCR₅₀, HiSCR₇₅, HiSCR₉₀, and HiSCR₁₀₀ responders, respectively, at Week 16. These summaries will be based on observed case data and will not consider the occurrence of intercurrent events.

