2.3 Study design and conduct

2.3.1 Study description

HS0003 is a Phase 3, randomized, double-blind, placebo-controlled, multicenter, pivotal study evaluating the efficacy and safety of bimekizumab in study participants with moderate to severe HS. Study participants meeting the inclusion criteria who do not meet any exclusion criteria will complete a Screening Period of 14 days to up to 5 weeks; a double-blind, 48-week Treatment Period comprising a 16-week Initial Treatment Period and 32-week Maintenance Treatment Period; and a 20-week Safety Follow-up (SFU) Period following the final injection of investigational medicinal product (IMP) if study participants do not enter a subsequent extension study (HS0005) or withdraw prematurely from treatment.

Study participants will be randomized in a 2:2:2:1 ratio (stratified by Hurley Stage and current antibiotic use) to 1 of 3 dose regimens of bimekizumab or placebo as shown in the schematic (Figure 2-1).

Figure 2-1: Study Schematic

HiSCR₅₀=a 50% reduction in the total abscess and inflammatory nodule count with no increase from Baseline in abscess or draining tunnel count;

IMP=investigational medicinal product; Q2W=every 2 weeks; Q4W=every 4 weeks

*Week 16 = primary endpoint (HiSCR₅₀ bimekizumab versus placebo)

a Study participant should discontinue from the study from Week 32 on if no partial response is achieved (partial response is defined as $\geq 25\%$ improvement in abscess and inflammatory nodule count relative to Baseline [Week 0] lesion values.)

b Study participants achieving an improvement of at least 25 % in abscess and inflammatory nodule count continue in HS0005 (Extension Study).

c 20-week Safety Follow-up (from last IMP injection) for any study participant who discontinues from study prior to Week 48, or who does not continue in HS0005.

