3 DATA ANALYSIS CONSIDERATIONS

3.1 General presentation of summaries and analyses

Statistical analysis and generation of tables, figures, study participants data listings, and statistical output will be performed using SAS Version 9.4 or higher. All tables and listings will use Courier New font size 9.

Descriptive statistics will be displayed to provide an overview of the study results. For continuous variables, descriptive statistics will include number of study participants with available measurements (n), mean, standard deviation (SD), median, minimum, and maximum.

For PRO continuous variables, descriptive statistics will also include variable score, absolute and percentage changes from baseline, Q1 and Q3, 10th, and 90th percentiles.

If no participants have data at a given time point, then only n=0 will be presented. The other descriptive statistics will be left blank. If n < 3 then the n, minimum, and maximum only will be presented. The other descriptive statistics will be left blank. If n = 3 n, mean, median, minimum and maximum will be presented only. The other descriptive statistics will be left blank.

For categorical variables, the number and percentage of study participants in each category will be presented. Unless otherwise noted, the denominator for percentages will be based on the number of study participants included in the respective analysis set. Study participants with missing data will be accounted for using the following approaches:

- For summaries of demographics and Baseline characteristics: percentages will be based on all study participants in the analysis set and a “Missing” category (corresponding to study participants with missing data for the variable being summarized) will be included as the last row in the list of categories being summarized.
- For summaries of efficacy and safety endpoints, unless otherwise specified: percentages will be based only on those study participants with observed data for the variable being summarized. As the denominator may be different from the number of study participants in the analysis set being considered, the denominator will be displayed in the table. The general format for displaying this will be “n/Nsub (%).”

Percentages will be presented to 1 decimal place. If the percentage is 100%, a decimal will not be presented. If the count is 0, the percentage will not be presented. Typically, the % sign will be presented in the column header, but not with each individual value.

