4.2.1.4 Missing Data Overview and Summary

In summary, the approaches listed below will be used in this study for handling missing data for efficacy endpoints as appropriate:

- **NRI:** Participants who have missing data at the timepoint of interest are treated as though they did not respond to the treatment. This approach is also referred to as Composite Estimand (NRI).
- **Multiple Imputation (MI) – MCMC / Monotone Regression:** Using multiple imputation methodology, intermittent missing data are imputed based on the MCMC method, and monotone missing data are imputed using monotone regression.
- **MI–MCMC / Reference-based imputation:** Using multiple imputation methodology, intermittent missing data are imputed based on the MCMC method, and monotone missing data are imputed using an imputation model based on placebo (reference) data.
- **LOCF:** Post-Baseline missing data are imputed by carrying forward the last available observation (including Baseline).
- **Tipping point analyses:** Assumptions will be made about average outcomes among the subsets of participants who prematurely discontinued study treatment. Various “delta adjustments” will be made to the assumed responses among missing data in each treatment arm with varying degrees of plausibility in order to identify assumptions about the missing data under which the conclusions change (O’Kelly, 2014). Then, the plausibility of such assumptions is discussed.
- **Observed case (OC):** Missing data are not imputed. Only participants with available data who have not discontinued study treatment at the given timepoint are considered. Study participants with missing data or who have prematurely discontinued study treatment will be treated as missing.

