Kaplan-Meier plots of time to HiSCR responses will be presented by treatment group. In these Kaplan-Meier plots, the line will start at 0 (since there are no responders at Week 0) and will increase over time, representing time to achieving the response.

The median time to response, including the 2-sided 95% confidence interval, will be calculated for each treatment.

8.4.1.3 HiSCR_{25} , HiSCR_{50} , HiSCR_{75} , HiSCR_{90} , and HiSCR_{100} response at both Weeks 16 and 48

See Section 8.4.1.1 for the derivation of HiSCR response.

The number and percentage of HiSCR_{25} , HiSCR_{50} , HiSCR_{75} , HiSCR_{90} , and HiSCR_{100} responders at both Weeks 16 and 48 will be summarized based on the RS and MS.

Missing data for the above summaries will be handled using NRI. That is, participants are counted as responders only if they have an observed HiSCR at both Weeks 16 and 48 and have no intercurrent events through Week 48. Otherwise, they are treated as not responding.

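### Progression of Week 16 partial responders is summarized only on observed cases with intercurrent events ignored, so the percentages can only equal or exceed a fixed-denominator count

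*SAP*

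**What the plan says.** The subset in Section 8.4.1.6 is the "subset of participants in the MS that are partial responders but not" HiSCR responders of the given level at Week 16. Their later response is summarized by treatment group and visit, under this rule: "These summaries will be based on observed case data and will not consider the occurrence of intercurrent events".

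Three other provisions determine what that produces.

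- Section 4.2.1.4 defines observed case: "Only participants with available data who have not discontinued study treatment at the given timepoint are considered".
- Section 3.1 sets the default denominator for efficacy summaries: "percentages will be based only on those study participants with observed data for the variable being summarized". The denominator is displayed with the percentage.
- Section 2.3.1, Figure 2-1 note a: "Study participant should discontinue from the study from Week 32 on if no partial response is achieved". Partial response there means at least 25% improvement in AN count relative to Baseline.

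Elsewhere the SAP handles comparable endpoints differently. Section 4.2.1.3 says "For other binary efficacy endpoints, missing data will be imputed using the same method as the primary efficacy endpoint", which means nonresponse after an intercurrent event and multiple imputation for the rest. Section 8.4.1.3 uses nonresponder imputation: "participants are counted as responders only if they have an observed HiSCR at both Weeks 16 and 48" and have had no intercurrent event through Week 48. Section 8.4.1.5 treats an intercurrent event as loss of response.

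**The concern.** The quantity of interest is the share of Week 16 partial responders who convert with continued dosing. An observed-case percentage answers a narrower question: the share among those still contributing data at that visit. If the people who leave are mostly non-progressors, the percentage can rise over time without a single further responder.

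Two features push in that direction. The schematic asks participants without a partial response to leave from Week 32 on. Setting intercurrent events aside also lets a HiSCR reached after systemic antibiotic rescue count as progression, although the SAP's composite strategy would call it nonresponse.

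The resulting figures would sit in the same report as Sections 8.4.1.3 and 8.4.1.5, which treat the same events as failure. The tables could not be read side by side, and Section 8.4.1.6 gives no reason for the exception.

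**Working it through.** The SAP states no figure for this summary, so there is none to reproduce. The check is on direction first, then on possible size.

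**Who leaves under note a.** Under Section 8.2.1, HiSCR50 needs at least a 50% reduction in AN count, and the higher levels need more. A participant below 25% improvement cannot meet any of them. Any subset member removed under the rule is therefore a known non-progressor at that point.

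**Direction.** For one arm at one visit, let

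- N = members of the Section 8.4.1.6 subset,
- R = observed responders with no intercurrent event,
- g = observed responders who have had an intercurrent event,
- m = subset members not contributing at the visit.

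Fixed-denominator count (intercurrent event or missing = non-progression): R/N.

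Section 8.4.1.6 as written: (R + g)/(N − m).

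Since R + g ≥ R and N − m ≤ N, the second is never smaller. It is strictly larger if g > 0, or if m > 0 with R > 0. If m = 0 and g = 0 the two are equal.

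**Treatment stops.** Section 3.9 says: "An intercurrent event is defined as receipt of systemic antibiotic rescue medication or discontinuation of study treatment due to an AE or lack of efficacy". Section 4.2.1.4 drops anyone who has stopped treatment from an observed-case summary, whereas Section 8.4.1.6 says intercurrent events, which include some of those stops, are not considered. Post-stop data could be programmed as out (adding to m) or in (possibly adding to g). The inequality holds either way, but the tables would differ.

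**Size, on assumed inputs.** The SAP gives no subset size, progression rate, attrition or rescue rate. Take N = 100 and R = 40, so R/N = 40%.

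| Left by the visit (m) | g = 0 | g = 5 |
|---|---|---|
| 0 | 40/100 = 40.0% | 45/100 = 45.0% |
| 5 | 40/95 = 42.1% | 45/95 = 47.4% |
| 10 | 40/90 = 44.4% | 45/90 = 50.0% |
| 20 | 40/80 = 50.0% | 45/80 = 56.25% |
| 30 | 40/70 = 57.1% | 45/70 = 64.3% |

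Letting R/N run from 30% to 50% and m from 5 to 30:

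- With g = 0 the excess runs from 1.6 points (30/95 = 31.6%) to 21.4 points (50/70 = 71.4%).
- With g = 5 it runs from 6.8 points (35/95 = 36.8%) to 28.6 points (55/70 = 78.6%).

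None of these percentages is a forecast for this trial.

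**The case against.** The observed-case basis is stated openly, and a specific provision overrides the general rule in Section 4.2.1.3. The programmer knows which summary to produce, apart from the handling of post-stop data. Section 3.1 already has the denominator displayed, so a reader can see it shrink. Section 8.4.1.1 presents by-visit HiSCR both as observed and with intercurrent events and missing data handled, although for the whole population and not for this subset. The endpoint has no test, is absent from the nominal p-values in Section 8.5 and lies outside the hierarchy. Nonresponder imputation has its own bias: someone missing for an unrelated reason may have progressed. All of this stands and limits the weight of the point.

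A reader might also infer that the study removes non-responders from Week 32, so that late percentages are inflated by design. The documents do not support that.

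- The rule concerns absence of a partial response. A participant who stays between 25% and 50% improvement is a HiSCR50 non-progressor but remains in the study and in the denominator. Within this subset, the rule reaches only those who fall back below 25%.
- If the note means that a partial response was never achieved, it reaches nobody in the subset, since all had one at Week 16. The words about Week 32 onward, and the definition of partial response at a particular timepoint in Section 8.4.1.6, favour a visit-by-visit reading. The operating detail belongs to the protocol, which is not at hand.
- Visits before Week 32 are untouched by the rule. Only other dropout and intercurrent events act there.
- Nothing in the SAP supports any particular attrition rate. That arms with more stops would look better also holds only if those who stop are mainly non-progressors.

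**Conclusion.** The point holds in a limited form. Against a fixed-denominator count that treats intercurrent events and missing data as non-progression, the Section 8.4.1.6 percentage can only be equal or higher, under either reading of note a. This direction does not carry over to a comparison with multiple imputation, which could credit some missing participants with a response.

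The size cannot be computed from the SAP. Under the assumed 40% progression with no responses after intercurrent events, the excess is about 2 points at 5% attrition and 17 points at 30%. It is zero with no leavers and no intercurrent events.

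The consequence is for interpretation and for consistency with Sections 8.4.1.3 and 8.4.1.5. Type I error and the confirmatory conclusions are not affected. It is a worthwhile improvement at low cost.

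**What to change.** In Section 8.4.1.6, add a summary that keeps all Week 16 partial responders in the relevant MS subset as the denominator at every visit. Count a participant as a non-progressor after an intercurrent event, and after leaving for lack of partial response. Name the latter explicitly, because the SAP does not say whether such a departure is recorded as discontinuation for lack of efficacy. For other missing data, specify one method: nonresponder imputation as in Section 8.4.1.3, or the imputation of Section 4.2.1.3.

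Keep the observed-case table as supportive, with the number observed at each visit. State whether data after treatment discontinuation enter it, so that Section 8.4.1.6 agrees with the observed-case definition in Section 4.2.1.4.

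The cost is some SAP wording, one more table and percentages that are likely to look less favourable. If nonresponder imputation is chosen, note that it may understate progression for participants missing for unrelated reasons. No change to the discontinuation rule is proposed.
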